16.3 Evaluation of Response

Time point response assessments will be performed according to the 2018-NCCN follow-up guidelines for patients with advanced HNC (63), up to 24 months after I-PDT. To determine time point response criteria, refer to **Table 1** below.

Target Lesions Non-Target Lesions		New Lesions	Overall Response	
CR	CR	No	CR	
CR	Non-CR/Non-PD	No	PR	
CR	Not evaluated	No	PR	
PR	Non-PD or not all evaluated	No	PR	
SD	Non-PD or not all evaluated	No	SD	
Not all evaluated Non-PD		No	NE	
PD Any		Yes or No	PD	
Any PD		Yes or No	PD	
Any Any		Yes	PD	

Table 1 Time Point Response Criteria (+/- non-target disease)

Table 2. Time Point Response Criteria (non-target disease only)

Non-Target Lesions	New Lesions	Overall Response	
CR	No	CR	
Non-CR/non-PD	No	Non-CR/non-PD ¹	
Not all evaluated	No	NE	
Unequivocal PD	Yes or No	PD	
Any	Yes	PD	

Non-CR/non-PD is preferred over SD for non-target disease since SD is used as endpoint for assessment of efficacy in trials so to assign this category when no lesions can be measured is not advised.

The best overall response is the best response recorded from the start of study treatment until follow-up is completed or the participant goes off study (the end of treatment taking into account any requirement for confirmation).

• Symptomatic Deterioration: Participants with global deterioration of health status requiring study withdrawal without objective evidence of disease progression at that time, and not related to study treatment or other medical conditions should be reported as progressive disease due to "symptomatic deterioration." Every effort should be made to document objective progression even after discontinuation of treatment due to symptomatic deterioration. Symptomatic deterioration that may lead to study withdrawal includes, but is not limited to, symptoms such as:

- Weight loss > 10% of body weight.
- o Worsening of disease-related symptoms (e.g., worsening dyspnea, increasing pain/increasing requirement for narcotic analgesics).
- \circ Decline in performance status of > 1 level on ECOG scale.

16.4 Guidelines for Evaluation of Measurable Disease

All baseline evaluations should be performed as closely as possible to the beginning of treatment and never more than 4 weeks before the beginning of the treatment.

The same method of assessment and the same technique should be used to characterize each identified and reported lesion at baseline and during follow-up. Imaging-based evaluation is preferred to evaluation by clinical examination unless the lesion(s) being followed cannot be imaged but are assessable by clinical exam.

• Conventional CT and MRI: This guideline has defined measurability of lesions on CT scan based on the assumption that CT slice thickness is 5 mm or less. If CT scans have slice thickness greater than 5 mm, the minimum size for a measurable lesion should be twice the slice thickness. MRI is also acceptable in certain situations.

17.0 Safety Evaluation

17.1 Adverse Events

An adverse event or adverse experience (AE) is any untoward medical occurrence associated with the use of a drug in humans, whether or not considered drug related. Therefore, an AE can be ANY unfavorable and unintended sign (including an abnormal laboratory finding), symptom, or disease temporally associated with the use of a medicinal (investigational) product, whether or not considered related to the medicinal (investigational) product (attribution of 'unrelated', 'unlikely', 'possible', 'probable', or 'definite').

An AE is considered "unexpected" if it is not listed in the investigator brochure or is not listed at the specificity or severity that has been observed; or if an investigator brochure is not required or available, is not consistent with the risk information described in the general investigational plan in other study-related documents.

17.1.1 DIAGNOSIS VERSUS SIGNS AND SYMPTOMS

If known, a diagnosis should be recorded on the CRF rather than individual signs and symptoms (e.g., record only liver failure or hepatitis rather than jaundice, asterixis, and elevated transaminases). However, if a constellation of signs and/or symptoms cannot be clinically characterized as a single diagnosis or syndrome at the time of reporting, each individual event should be recorded as an AE or SAE on the CRF. If a diagnosis is subsequently established, it should be reported as follow-up information.

17.1.2 ADVERSE EVENTS OCCURRING SECONDARY TO OTHER EVENTS

In general, AEs occurring secondary to other events (e.g., cascade events or clinical sequelae) should be identified by their primary cause. For example, if severe diarrhea is known to have resulted in dehydration, it is sufficient to record only diarrhea as an AE or SAE on the CRF.

13MAR2023; SRC 18SEP2023; IRB 15NOV2023

However, clinically significant AEs occurring secondary to an initiating event that are separated in time should be recorded as independent events on the CRF. For example, if a severe gastrointestinal hemorrhage leads to renal failure, both events should be recorded separately on the CRF.

17.1.3 ABNORMAL LABORATORY VALUES

Only clinically significant laboratory abnormalities that require active management will be recorded as AEs or SAEs on the CRF (e.g., abnormalities that require study drug dose modification, discontinuation of study treatment, more frequent follow-up assessments, further diagnostic investigation, etc.).

If the clinically significant laboratory abnormality is a sign of a disease or syndrome (e.g., alkaline phosphatase and bilirubin 5 x the upper limit of normal associated with cholecystitis), only the diagnosis (e.g., cholecystitis) needs to be recorded on the Adverse Event CRF.

If the clinically significant laboratory abnormality is not a sign of a disease or syndrome, the abnormality itself should be recorded as an AE or SAE on the CRF. If the laboratory abnormality can be characterized by a precise clinical term, the clinical term should be recorded as the AE or SAE. For example, an elevated blood potassium level of 7 mEq/L should be recorded as "hyperkalemia."

Observations of the same clinically significant laboratory abnormality from visit to visit should not be repeatedly recorded as AEs or SAEs on the CRF, unless their severity, seriousness, or etiology changes.

17.1.4 PREEXISTING MEDICAL CONDITIONS (BASELINE CONDITIONS)

A preexisting medical condition should be recorded as an AE or SAE only if the frequency, severity, or character of the condition worsens during the study. When recording such events on an Adverse Event CRF, it is important to convey the concept that the preexisting condition has changed by including applicable descriptors (e.g., "more frequent headaches").

17.2 Grading and Reporting Adverse Events

17.2.1 GRADING AND RELATIONSHIP TO DRUG

The descriptions and grading scales found in the CTEP Version 5.0 of the NCI Common CTCAE will be utilized for AE reporting. CTEP Version 5.0 of the CTCAE is identified and located at:

http://ctep.cancer.gov/protocolDevelopment/electronic applications/ctc.htm.

AEs not covered by specific terminology listed should be reported with common medical terminology, and documented according to the grading scales provided in the CTCAE Version 5.

The relationship of event to study drug will be documented by the Investigator as follows:

- Unrelated: The event is clearly related to other factors such as the participant's clinical state, other therapeutic interventions or concomitant drugs administered to the participant.
- Unlikely: The event is doubtfully related to investigational agent(s). The event was most likely related to other factors such as the participant's clinical state, other therapeutic interventions, or concomitant drugs.

- **Possible:** The event follows a reasonable temporal sequence from the time of drug administration, but could have been produced by other factors such as the participant's clinical state, other therapeutic interventions or concomitant drugs.
- **Probable:** The event follows a reasonable temporal sequence from the time of drug administration, and follows a known response pattern to the study drug. The event cannot be reasonably explained by other factors such as the participant's clinical state, therapeutic interventions or concomitant drugs.
- **Definite:** The event follows a reasonable temporal sequence from the time of drug administration, follows a known response pattern to the study drug, cannot be reasonably explained by other factors such as the participant's condition, therapeutic interventions or concomitant drugs; AND occurs immediately following study drug administration, improves upon stopping the drug, or reappears on re-exposure.

17.3 Reporting Adverse Events

Routine AEs occurring between the start date of intervention until 30 days after the last intervention, or until the event has resolved, the study participant is lost to follow-up, the start of a new treatment, or until the study investigator assesses the event(s) as stable or irreversible, will be reported. New information will be reported after it is received.

Table 1 Guidelines for Routine Adverse Event Reporting for Phase 1 Studies (Regardless of Expectedness)

Attribution	Grade 1	Grade 2	Grade 3	Grade 4
Unrelated	X	X	X	X
Unlikely	X	X	X	X
Possible	X	X	X	X
Probable	X	X	X	X
Definite	X	X	X	X

Routine AEs occurring between the start of intervention until 30 days after the last intervention or until the event has resolved, stabilized, death, or a new treatment is started, whichever comes first, will be reported. New information will be reported after it is received.

Pinnacle Biologics, Inc. Bannockburn IL, will be receiving copies of all the reports (de-identified).

17.4 Serious Adverse Events

A serious adverse event (SAE) is any adverse event (experience) that in the opinion of either the investigator or sponsor results in ANY of the following:

- Death.
- A life-threatening adverse event (experience). Any AE that places a participant or participants, in the view of the Investigator or sponsor, at immediate risk of death from the reaction as it occurred. It does NOT include an AE that, had it occurred in a more severe form, might have caused death.
- Inpatient hospitalization or prolongation of existing hospitalization (for > 24 hours).

- A persistent or significant incapacity or substantial disruption of the ability to conduct normal life functions.
- A congenital anomaly or birth defect.
- Important Medical Event (IME) that, based upon medical judgment, may jeopardize the participant and may require medical or surgical intervention to prevent one of the outcomes listed above.

17.4.1 REPORTING SERIOUS ADVERSE EVENTS

All new SAEs occurring from the date the participant signs the study consent until 30 days after the last intervention or a new treatment is started, whichever comes first, will be reported. The RPCI SAE Source Form is to be completed with all available information, including a brief narrative describing the SAE and any other relevant information.

SAEs occurring after the 30 day follow-up period that the investigator determines to be possibly, probably or definitely related to the study intervention should be reported.

SAEs that are unexpected and possibly, probably or definitely related must be reported as an Unanticipated Problem. Please refer to **Section 17.6** for details on reporting Unanticipated Problems.

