10.3 Definition of Dose-Limiting Toxicity

Dose Limiting Toxicities will include:

Any adverse events (AEs) that are \geq grade 4 that are possibly, probably, or definitely related to the I-PDT, by recording the occurrence of AE during the first 30 days post final I-PDT treatment using the revised the National Cancer Institute (NCI) Common Terminology Criteria for Adverse Events version 5.0 (CTCAE v5.0). Dose Limiting Toxicities will be evaluated for 30 days post final I-PDT day.

If participants experience DLTs, further I-PDT sessions will be held until DLT resolution as well as after porfimer sodium clearance.

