10.5 Treatment Discontinuation

All subjects who discontinue due to an AE must be followed until the event resolves or stabilizes. Appropriate medical care should be provided until signs and symptoms have abated, stabilized, or until abnormal laboratory findings have returned to acceptable or pre-study limits. The final status of the AE will be reported in the subject's medical records and the appropriate eCRF.

Reasons for treatment discontinuation should be classified as follows:

- Death
- Progressive disease
- Treatment-related toxicity
- Toxicity unrelated to treatment
- Investigator judgment
- The Investigator may withdraw a subject if, in his/her judgment, it is in the subject's best interest to do so.
- Noncompliance
- Subject voluntary withdrawal
 - A subject may withdraw from the study at any time, for any reason. If a subject discontinues treatment, an attempt should be made to obtain information regarding the reason for withdrawal.
- Early withdrawal of subject(s)
- Sponsor decision

Subjects who are unavailable for follow-up evaluations should be classified as lost to follow-up for 1 of the following reasons:

- Lost to follow-up: For a subject to be considered lost to follow-up, the investigator must make two attempts to re-establish contact with the subject. The attempts to re-establish subject contact must be documented (e.g., certified letter).
- Death: Date and cause of death will be recorded for those subjects who die within 30 days after treatment (telephone contact is acceptable).

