11.5 Evaluations Performed at 1st Post-Operative Clinic Visit

This visit will be scheduled 1 to 4 weeks post I-PDT and will include:

- Physical examination, including vital signs (i.e., temperature, heart rate, respiratory rate, blood pressure, body weight, and pain assessment using a verbal score of 0-10)
- Hematology (i.e., CBC (with auto differential), ANC, and platelets)
- Chemistry (i.e., AST, ALT, total bilirubin, alkaline phosphatase, creatinine, potassium, glucose, and calcium)
- ECOG Performance Status
- Adverse events
- UW QoLQ v4
- Research blood draws (Optional) #

Performed as per PI discretion if later I-PDT courses are deemed necessary as per Section 10.4.

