17.5 Follow-Up for Serious Adverse Events

All related SAEs should be followed to their resolution, until the study participant is lost to follow-up, the start of a new treatment, or until the study investigator assesses the event(s) as stable or irreversible. New information will be reported when it is received.

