Appendix D Schedule of Procedures and Observations if Only I-PDT Course is Necessary

Evaluation	Baseline ¹	Pre- Operative	Day of Treatment	Day 1 Post Treatment	1-week Post- treatment	Optional I-PDT Course 2 Within 2-3 Weeks of Day 0 ¹⁷	Clinic Visit ^{2,2a}	30- Day Post I- PDT ¹⁴	Optional I-PDT Treatment additional 2 or 3 At least 6 Weeks after last I-PDT Session ¹⁸	Follow- Up
Informed Consent	X									
Medical History	X								X	
Physical Exam/ Vital signs & pain assessment using a verbal score 0-10 ³	X				X		X	X	X	X
Hematology ⁴ and Chemistry ⁵	X				X		X	X	X	
Research Blood Draws ⁶			X		X		X	X	X	
Pregnancy Test (Urine)	X								X	
ECOG Performance Status	X		X		X		X	X	X	X
UW-QoLQ v. 4 ¹⁵	X				X		X	X	X	X
Standard Imaging of the head and neck with CT or MRI, for RECIST v11.1	X ⁷								X	X8
Treatment planning	X								X	
Porfimer Sodium administration and Vital Signs		X ⁹							X	
Intraoperative Ultrasound			X						X	
If possible, intraoperative CT or other clinically approved radiological imaging			X^{10}			X ¹⁰			X^{10}	
Interstitial PDT (I-PDT) 16			X^{11}			X ¹¹			X ¹¹	
Concomitant Medications	X ¹²		X							
Adverse Events ¹³			X		X		X	X		

Notes:

- * The I-PDT procedure is termed a "course".
 - 1. Performed within 8 weeks prior to porfimer sodium.
 - Performed at Day 1 of SOC therapy.
 If later 2nd and 3rd I-PDT courses are deemed necessary per the physician (see Section 10.4), please refer to Appendix D 1 for treatment, procedure, and test scheduling.
 - 3. Temperature, heart rate, respiratory rate, blood pressure, body weight and, height, Height collected at baseline only. Refer to Section 11.2.
 - 4. Hematology (i.e., CBC (with auto differential), ANC, and platelets). Refer to Section 11.2.
 - 5. Chemistry (i.e., AST, ALT, total bilirubin, alkaline phosphatase, creatinine, potassium, glucose, and calcium). Refer to Section 11.2.
 - 6. This is optional. Refer to immune markers Section 11.8 (1, 10 mL green-top tube).
 - 7. Standard tumor staging performed within 4 weeks, and at least 14 business days prior to I-PDT. If possible, the imaging will include temporary fiducial markers that will be affixed to skin. Refer to Section 11.2.
 - 8. CT scans at 10 to 12 weeks post SOC therapy and as clinically indicated following the NCNN 2018 guidelines.
 - 9. Infusion will occur 48 hours ± 8 h prior to illumination. Vitals are to be taken immediately after injection and after 15 minutes.

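### Three adverse-event windows are left unreconciled, and the one in Sections 17.3 and 17.4.1 can end reporting inside the 30-day DLT window if standard-of-care therapy starts early

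*Combined protocol and SAP*

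**What the plan says.** Three periods for recording adverse events appear in the combined protocol and SAP.

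- **30 days after the final I-PDT.** Section 8.1 sets this for the primary endpoint. Section 10.3 defines DLTs (related events of grade 4 or higher) "by recording the occurrence of AE during the first 30 days post final I-PDT treatment" and adds: "Dose Limiting Toxicities will be evaluated for 30 days post final I-PDT day". Neither makes an exception for a new treatment.
- **The earlier of 30 days or a new treatment.** Section 17.4.1 reports SAEs "until 30 days after the last intervention or a new treatment is started, whichever comes first, will be reported". Section 17.3 sets the same 30-day limit for routine AEs, with this ending: "or until the event has resolved, stabilized, death, or a new treatment is started, whichever comes first, will be reported".
- **30 days after the first SOC treatment.** Section 19.3 uses this anchor, or the last I-PDT day if no SOC is given. Appendix D notes 13 and 14, and the AE-period note in Appendix D 1 (note M), also anchor to SOC.

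On timing, Section 11.5 says of the first post-operative clinic visit: "This visit will be scheduled 1 to 4 weeks post I-PDT and will include". Appendix D note 2 says of its Clinic Visit column: "Performed at Day 1 of SOC therapy". Appendix D 1 places SOC in the Clinic Visit column.

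On follow-up, Section 17.5 says: "All related SAEs should be followed to their resolution, until the study participant is lost to follow-up, the start of a new treatment". Section 10.5 says: "All subjects who discontinue due to an AE must be followed until the event resolves or stabilizes".

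**The concern.** Table 2 of Section 10.4 decides on DLT counts in groups of three and six. Those counts are only as complete as the event reporting behind them. Section 17 is where reporting of AEs and SAEs is set out, and its stopping rule is shorter than the window in the DLT definition.

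If SOC begins in week 2, one person following Section 17.4.1 could stop reporting new SAEs that day. Another, following Section 10.3, would continue to day 30, and a third, following Appendix D note 13, would continue for 30 days after SOC began. All three would be following the protocol. The observation period could then differ between patients according to how soon SOC starts. Section 19.6 counts every treated subject as evaluable for toxicity, so a patient with a shortened window would still count in full.

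This is separate from the choice of anchor in Section 19.3. Re-anchoring that section to I-PDT would leave the cut-off in Sections 17.3 and 17.4.1 in place.

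**Working it through.** **The plan's own figure.** Section 4.0 gives a maximum of 12 evaluable participants as four cohorts of 3. Two dose levels (1 and -1) with 6 patients each give 2 × 6 = 12, which agrees. The conflict does not touch this number.

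**Can SOC start before day 30?** Section 11.5 puts the first clinic visit at 1 to 4 weeks, that is day 7 to day 28. If this is the Clinic Visit of Appendix D, it is also SOC Day 1. Appendix D 1 note N says Phase 1 patients are off treatment and on follow-up 30 days after the last I-PDT. It does not clearly bar SOC before then.

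**Days affected under the literal Section 17 rule** = 30 − SOC start day:

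| SOC start day | Days left outside reporting | Share of 30 days |
|---|---|---|
| 7 | 23 | 77% |
| 14 | 16 | 53% |
| 21 | 9 | 30% |
| 28 | 2 | 7% |

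**Do other clauses fill those days?**

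- The late-SAE clause in 17.4.1 covers related SAEs only after the 30-day follow-up period. It does not name the days between SOC start and day 30.
- Sections 17.6 to 17.8 have no stop at new treatment. Section 17.8 sends every SAE, related or not, to the manufacturer. Sections 17.6 and 17.7 cover unanticipated problems and unexpected related serious events. Many DLTs would be captured this way.
- A related grade 4 event that meets none of the seriousness criteria in 17.4 is a DLT under 10.3 but is not reached by these routes.

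**Worst-case illustration.** A level passes Table 2 with at most 1 DLT in 6. Two or more in the first three already rules that out, so the pass chance is P = (1 − q)^6 + 6q(1 − q)^5, where q is the captured DLT risk. The assumptions, none of them from the documents, are a true 30-day risk of 0.30, onset uniform over 30 days, SOC on the same day in every patient and nothing captured afterwards. Then q = 0.30 × SOC day / 30.

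| Reporting ends | q | P(level passes) |
|---|---|---|
| Day 30 (full window) | 0.30 | 0.420 |
| Day 28 | 0.28 | 0.464 |
| Day 21 | 0.21 | 0.631 |
| Day 14 | 0.14 | 0.800 |
| Day 7 | 0.07 | 0.939 |

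For assumed true risks of 0.20 and 0.40, the range from full capture to a day-7 cut-off is 0.655 to 0.971 and 0.233 to 0.899. With a constant hazard in place of uniform onset, the 0.30 case gives 0.769 at day 14 and 0.923 at day 7.

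**The case against.** A reader might infer that collection simply closes when SOC starts and that DLTs in the remaining days come under no rule. The documents do not support that.

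- Sections 8.1 and 10.3 independently require the full 30 days, and Section 19.7 describes continuous monitoring that includes the 30-day safety follow-up.
- Section 19.3, Appendix D note 13 and the matching Appendix D 1 note carry AE recording past SOC start. The Appendix D AE row is marked at the Clinic Visit and again in the 30-Day column.
- Sections 17.6 to 17.8 would bring in many SAEs regardless of new treatment.

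Other steps are also open to challenge. The term new treatment is undefined, and SOC is a row in the study's own Appendix D 1 schedule, so the clause may not be meant to include it. Column order in Appendix D does not show that SOC precedes day 30, because note 14 anchors the 30-Day column to the first SOC day. Day 7 is the weakest case: Section 11.5 does not mention SOC, and Appendix D has a separate 1-week column before the Clinic Visit. Section 9.0 describes what patients would otherwise receive, not what follows I-PDT.

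The conflict between Sections 17.5 and 10.5 is narrow. Section 10.5 covers only subjects who discontinue because of an AE, and both sections allow follow-up to end once the event is stable. They differ mainly in the new-treatment ending.

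These objections stand against a claim of settled non-collection. They do not remove the conflict. The instructions differ, nothing says which governs, and one of them is shorter than the window that defines a DLT.

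**Conclusion.** The point holds as an unreconciled conflict among three windows. If SOC is a new treatment and Sections 17.3 and 17.4.1 are applied literally, AE and SAE reporting under those sections stops inside the DLT window whenever SOC starts before day 30. About 2 to 23 of the 30 days could be affected, on the further reading that SOC starts at the clinic visit of Section 11.5. The gap is clearest for non-serious grade 4 events, which Sections 17.6 to 17.8 do not pick up.

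With at most 12 patients, a single missed DLT could change a Table 2 decision and so the recommended irradiance. How likely that is cannot be read from the documents. The rise from 0.420 to 0.800 with SOC on day 14, and the day-7 figure, describe a worst case with no capture after SOC, which other sections contradict. They should not be quoted as expected error rates.

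**What to change.** 1. In Sections 17.3 and 17.4.1, remove the new-treatment cut-off for the period through day 30 after the final I-PDT. All AEs and SAEs are then recorded for the whole window of Sections 8.1 and 10.3, whether or not SOC has started.
2. Record the SOC start date and flag events with onset after it, so that attribution can be reviewed.
3. Align Appendix D notes 13 and 14 and the AE-period note in Appendix D 1, so that an AE assessment at day 30 after the final I-PDT is explicit. Correct the Appendix D 1 note letters in the same edit: the AE row points to O, but the AE-period text stands under M.
4. In Section 17.5, reconcile the new-treatment ending with Section 10.5 for related SAEs.

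None of this requires a decision on when SOC should begin. The cost is wording in these sections and notes, plus attribution of some SOC-related events that would now be collected. Where the 30-Day column is anchored to SOC, an added AE check at I-PDT day 30 may be needed, for example by telephone.

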10.4 Dose Escalation/Finding Schema

The FDA approved porfimer sodium dose (2 mg/kg) will not change. We will aim to deliver light fluence rate of ≥ 8.6 mW/cm² and fluence of ≥ 45 J/cm² to 100% of the CTV (dose level 1), as much as possible. Dose level -1 will ≥ 5.0 mW/cm² and fluence of ≥ 45 J/cm² to 100% of the CTV.

Table 2. The study plan for finding optimal fluence rate in I-PDT with Photofrin in patients with LAHNC.			
Dose Level Number of patients with DLT at a given dose level		Decision rules	
Dose Level 1 (Starting): The maximum fluence rate, scaled for	0 out of 3	Enter 3 patients at Dose Level 1 : The laser fluence rate and fluence, scaled for human, which induced maximum photoreaction in the animal models	
human, which induced effective	1 out of 3	Enter 3 more patients at this Dose Level .	

photoreaction in the animal models.	≥2	Enter 3 patients at Dose Level -1 : The laser fluence rate and fluence, scaled for human, which induced minimal toxicity in the animal models.
	≤ 1 out of 6	This is generally the recommended Phase II dose rate/dose. At least 6 patients must be entered at the recommended Phase II dose.

In participants where their tumors may require more than one course of I-PDT for complete effective illumination of the CTV, up to three sessions of I-PDT may be performed, at the discretion of the treating physician. The FDA approves to administer up to three courses of PDT with Photofrin® each separated by at least 30 days in the treatment of esophageal and endobronchial cancer (http://www.photofrin.com/wp-content/uploads/2013/02/prescribing-info.pdf.). Therefore, treatment sessions in this study will be conducted at least 30-days apart. The porfimer sodium dose (2 mg/kg) will remain the same.

See Appendix D 1 for the Dose Escalation Schedule of Events. The date of the last I-PDT course will be used to determine the scheduling of the follow up SoC related to this study.

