19.3 Safety Analysis

The safety will be determined by recording the occurrence of SAE during the first 30 days post first SOC treatment day (or last I-PDT day if no therapeutic SOC is given) using the revised NCI Common Terminology Criteria for Adverse Events (CTCAE) version 5.0. Sequential boundaries will be used to monitor the SAE rate (64). The accrual will be halted if excessive numbers of SAEs are seen.

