19.6 Adverse Events

The frequency of toxicities will be tabulated by grade across all dose levels and cycles. All subjects who receive any study treatment will be considered evaluable for toxicity.

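### Section 19.3 starts the SAE count for the accrual halt at first standard of care rather than at I-PDT, and the reporting cut-offs in 17.3 and 17.4.1 do not match the 30-day DLT window

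*Combined protocol and SAP*

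**What the plan says.** The combined protocol and SAP gives several safety windows with different anchors.

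- **8.1 (primary endpoint):** adverse events (AEs) in the 30 days after the final I-PDT day.
- **10.3 (DLT definition):** grade 4 or higher, at least possibly related to I-PDT. "Dose Limiting Toxicities will be evaluated for 30 days post final I-PDT day". Table 2 in 10.4 acts on this count.
- **19.3 (accrual halt):** safety rests on "the occurrence of SAE during the first 30 days post first SOC treatment day", or on the last I-PDT day when no therapeutic SoC is given. Sequential boundaries apply, and "The accrual will be halted if excessive numbers of SAEs are seen".
- **17.4.1 (SAE reporting):** new SAEs from consent "until 30 days after the last intervention or a new treatment is started, whichever comes first, will be reported". A further clause adds "SAEs occurring after the 30 day follow-up period that the investigator determines to be possibly, probably or definitely related".
- **17.3 (routine AEs):** from start of intervention to 30 days after the last one, "or until the event has resolved, stabilized, death, or a new treatment is started, whichever comes first, will be reported".
- **Appendix D note 13 and Appendix D 1 note M:** AE reporting runs to 30 days (plus or minus 2) after the first SoC treatment. Note 14 appears to date the 30-day visit from first SoC as well, or from I-PDT if there is none.

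On when SoC starts, 10.4 says only that "The date of the last I-PDT course will be used to determine the scheduling of the follow up SoC related to this study". Section 11.5 puts the first post-operative clinic visit 1 to 4 weeks after I-PDT. Appendix D note 2 places its Clinic Visit on the first day of SoC, and Appendix D 1 marks SoC at its Clinic Visit. Note N, attached by its letter to the SoC row, has Phase 1 patients off treatment and in follow-up 30 days after the last I-PDT.

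**The concern.** The trial tests the safety of I-PDT, and the halt rule should count what happens after I-PDT. As written, for any patient who goes on to SoC, the 19.3 clock starts when SoC does. An SAE between I-PDT and SoC is then outside the halt count, including the life-threatening hemorrhage and emergency airway events that 19.7 singles out. The rule would instead count SAEs during the first month of SoC, some of them caused by SoC.

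The DLT rule does not fully cover this gap. A grade 3 bleed that leads to admission is serious under 17.4 but is not a DLT under 10.3. If it occurs before SoC, neither numerical rule counts it.

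The second issue is the new-treatment cut-off in 17.3 and 17.4.1. New treatment is not defined and SoC is not exempted. If SoC starts inside the 30 days, these sections stop before the DLT window does, while notes 13 and M continue past it. No text says which governs. Levels are decided on three to six patients, so one or two events can change a decision.

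**Working it through.** **Plan's own figure.** Two levels (1 and -1) with up to 6 patients each give 2 × 6 = 12, which equals the four cohorts of 3 in 4.0 and the maximum in 19.1. It reproduces.

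**Coverage of the 30 days after the last I-PDT.** Let SoC start on day s.

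- 10.3 covers 30 days in every case.
- 17.4.1, if SoC is a new treatment, covers min(s, 30) days.
- 19.3 covers 30 − s days if s < 30, none if s > 30, and all 30 if no SoC is given.

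| SoC start | 10.3 | 17.4.1 (SoC = new treatment) | 19.3 |
|---|---|---|---|
| none | 30 | 30 | 30 |
| day 7 | 30 | 7 | 23 |
| day 28 | 30 | 28 | 2 |
| after day 30 | 30 | 30 | 0 |

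Days 7 and 28 are the ends of the 11.5 visit range. Using them assumes that the Appendix D Clinic Visit is the 11.5 visit. The 19.3 gap does not need that assumption: it exists whenever SoC is given, and is largest when SoC waits past day 30. For SoC inside the window, the 17.4.1 period closes on the day the 19.3 period opens.

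**Effect on the halt.** Section 19.3 cites a reference for its boundaries but states no boundary values or target SAE rate, so the change in the chance of halting cannot be calculated.

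**Effect on Table 2, as illustration only.** This applies if events after SoC start were not counted. The DLT risk p, the onset pattern and the number of patients cut off are all assumed. A level is kept with at most 1 DLT in 6 (2 or more in the first 3 already rejects it).

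- Full observation, p = 0.30: 0.70^6 + 6 × 0.30 × 0.70^5 = 0.118 + 0.303 = 42.0%.
- A patient cut off on day 14 has observed risk r = p × f. Uniform onset gives f = 14/30 = 0.467 and r = 0.14. Early onset (80% by day 7, the rest uniform to day 30) gives f = 0.80 + 0.20 × 7/23 = 0.861 and r = 0.258.
- With two of six cut off, P(keep) = (1−p)^4(1−r)^2 + 4p(1−p)^3(1−r)^2 + (1−p)^4 × 2r(1−r). This gives 54.0% (uniform) or 45.1% (early).
- With all six cut off on day 14: 80.0% or 51.4%.
- With two of six cut off on day 28: 43.5% or 42.4%.

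**Opposite direction.** If notes 13 and M govern, SoC events judged possibly related to I-PDT may add to the count. With base risk 10% and an independent added risk of 5% to 20% in two of six patients, the chance of rejecting the level rises from 11.4% to between 14.5% and 24.4%. These inputs are also assumed.

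**The case against.** A reader might infer that, with SoC on day 14, a related grade 4 bleed on day 20 goes unreported and drops out of Table 2. The documents do not support that.

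- Section 17.8 requires every SAE, related or not, to go to the manufacturer within 1 business day, with no new-treatment cut-off.
- Unexpected related SAEs must also go forward as Unanticipated Problems under 17.4.1 and 17.6.1, and to FDA under 17.7 when its criteria are met. None of these sections ends at a new treatment.
- Table 2 rests on 10.3, which has its own instruction to record AEs for 30 days with no cut-off. Sections 8.1 and 19.7 say the same in substance.
- The AE rows in both schedules are marked at the Clinic Visit and at a later visit, and notes 13 and M carry collection past the start of SoC. This suggests the drafters did not mean SoC to end collection.
- Section 17.3 is less clear than 17.4.1: resolution and stabilization are end-points for following an existing event, not for closing the onset of new ones.
- Early SoC depends on equating two visits. Appendix D has a separate 1-week column, and note N points to 30 days.

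Section 19.6 ("All subjects who receive any study treatment will be considered evaluable for toxicity") does not strengthen the stronger reading either: it concerns tabulating toxicities, not evaluability for Table 2.

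It would also be wrong to say that 19.3 never counts from I-PDT, because it does when no SoC is given. Related grade 4 or higher bleeds and airway events still count under 10.3.

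All of this stands. It reduces the reporting issue to an unresolved conflict. It does not repair 19.3, whose anchor for SoC-treated patients is explicit and departs from 8.1 and 10.3.

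**Conclusion.** The point holds in two parts of different strength. First, the 19.3 halt count, read literally, omits SAEs between I-PDT and SoC in every patient who receives SoC, and all 30 days after I-PDT if SoC starts later than day 30. This follows from the text alone. Second, 17.3 and 17.4.1 stop short of the 10.3 window if SoC counts as a new treatment and starts before day 30. Both conditions are assumptions, and notes 13 and M conflict with the cut-off.

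Loss of DLTs from Table 2 is possible but not shown. The illustrated shift runs from under 1 percentage point to 38 points, depending on inputs the documents do not give, and the direction can reverse. The size of any effect on either decision rule is therefore unknown. The windows should be aligned because safety is the primary endpoint and the correction is cheap. Confidence is medium.

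**What to change.** 1. In 19.3, run the SAE window for every patient from the first I-PDT (or porfimer dose) through 30 days after the last I-PDT. Starting at the first treatment matters because 10.4 allows up to three courses at least 30 days apart, and even the no-SoC fallback starts only at the last.
2. In 17.3 and 17.4.1, report all AEs and SAEs through day 30 after the last I-PDT whether or not SoC has started.
3. Date Appendix D notes 13 and 14 and Appendix D 1 note M from the last I-PDT.
4. Record the SoC start date to help attribution.

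The cost is wording plus one data item. The schedule already has a 30-day visit. The downside is that some SoC-caused events will be collected in the window and must be attributed. Deferring SoC to after day 30, or replacing patients not observed to day 30, is not needed for this correction: the first delays palliative treatment and the second may exceed the maximum of 12.
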